## 3.2 General study level definitions

### 3.2.1 Relative day

Relative day will be calculated based on the treatment received. Therefore, three relative days are defined, based on treatment with OC alone, PSL alone and the combination of OC and PSL.

The relative day of an event will be derived with the date of first dose of the treatment, as reference. For Padsevonil, this will be Day 1 in Sequence A and Day 18 in Sequence B. For OC alone this will be Day 34 in Sequence A and Day 1 in Sequence B. For the combination of PSL+OC the first dose is given on Day 13 in Sequence A and Day 30 in Sequence B

Relative days for an event or measurement occurring before the date of first dose of treatment are calculated as follows:

$$\text{Relative Day} = \text{Event Date} - \text{Date of First Dose of Treatment}$$

The relative day for an event or measurement occurring on the date of first treatment dose is 1. The relative day for an event or measurement occurring on or after the date of first treatment dose to the date of the last dose will be calculated as follows:

$$\text{Relative Day} = (\text{Event Date} - \text{Date of First Dose of Treatment}) + 1$$

For events or measurements occurring after the date of last treatment dose, relative day will be prefixed with '+' in the data listings and will be calculated as follows:

$$\text{Relative Day} = + (\text{Event Date} - \text{Date of Last Dose of Treatment})$$

There is no relative Day 0. Relative day will not be calculated for partial dates in cases where relative day is shown in a study participant data listing. In such cases, relative day should be presented as '--' in the relevant study participant data listing.

### 3.2.2 Study periods

For each study participant completing Part 1, the expected maximum duration of participation will be approximately 75 days with a maximum of 20 days exposure to investigational product (19 days exposed to PSL, (with or without OC) and one day exposed to OC only).

For each study participant completing Part 2, the expected maximum duration of participation is approximately 70 days with a maximum of 12 days exposure to investigational product (11 days exposed to PSL, (with or without OC) and one day exposed to OC only).

The various periods of the study are described below:

- Screening/Baseline Period (Day -28 to Day -1)

The Screening Period consists of a single Screening Visit, which will be conducted at the unit within 28 days prior to check-in for treatment period, and a Baseline Visit, which will be conducted at HMR, the clinical research unit (CRU) 1 day prior to treatment period (on Day -1). Study participants will check-in at the CRU on Day -1.

## **Part 1**

### ***Sequence A (Day 1 to Day 36)***

In Part 1, study participants enrolled in Treatment Sequence A will be administered PSL BID (up-titration to steady-state [400mg BID]) from Day 1 to Day 5, followed by a maintenance period from Day 6 to Day 12 with a single dose of OC administered on the morning of Day 13. A taper of PSL will occur from Day 15 to Day 19. Starting on Day 20, the study participants will then complete a 14-day Washout Period followed by a return to the clinic for the OC-only dosing on Day 34. A SFU Visit will occur between Day 41 and Day 44.

Treatment Sequence A consists of the “PSL+OC Period” followed by the “OC alone Period”.

### ***Sequence B (Day 1 to Day 36)***

In Part 1, study participants enrolled in Treatment Sequence B will be administered a single dose of OC on the morning of Day 1 followed by PK assessments that day and the next 2 days. The study participants will then complete a 14-day Washout Period followed by a return to the clinic for the OC+PSL dosing from Day 18 to Day 36 (OC to be administered on Day 30). Study participants will be administered PSL BID (up-titration to steady-state) from Day 18 to Day 22 followed by a maintenance period from Day 23 to Day 31. A taper of PSL will occur from Day 32 to Day 36. An SFU Visit will occur between Day 43 and Day 46.

Treatment Sequence B consists of the “OC alone Period” followed by the “PSL+OC Period”.

## **Part 2**

### ***Sequence A (Day 1 to Day 28)***

In Part 2, all study participants enrolled in Treatment Sequence A will be administered PSL 100mg BID on Day 1, with titration to 200mg BID for Day 2 to Day 8. A single dose of OC is administered on the morning of Day 9, at which time PSL is at steady-state. To taper, 100mg BID of PSL will be given on Day 11. Starting on Day 12, the study participants will then complete a Washout Period for 14 days followed by a return to the clinic for the OC-only Period on Day 25 (OC dosing on Day 26). An SFU Visit will occur between Day 33 and Day 40.

Treatment Sequence A consists of the “PSL+OC Period” followed by the “OC alone Period”.

### ***Sequence B (Day 1 to Day 28)***

In Part 2, all study participants enrolled in Treatment Sequence B will be administered a single dose of OC on the morning of Day 1 followed by PK assessments that day and the next 2 days. The study participants will then complete a 14-day Washout Period followed by a return to the clinic for the OC+PSL dosing from Day 18 to Day 28 (OC to be administered on Day 26, at which time PSL is at steady state). Study participants will be administered PSL 100mg BID of PSL will be given on Day 28. An SFU Visit will occur between Day 35 and Day 42.

Treatment Sequence B consists of the “OC alone Period” followed by the “PSL+OC Period”.

The end of the study is defined as the date of the last scheduled procedure shown in the Schedule of Activities for the last study participant.

### **3.3 Definition of Baseline values**

In either study part, Baseline will be the last non-missing value prior to first dosing on Day 1 (PSL dosing in Treatment Sequence A or OC dosing in Treatment Sequence B). Scheduled or unscheduled measurements can be used as the Baseline value.

If a measurement is repeated at Baseline and is obtained prior to dosing, then the last available measurement will be used as the Baseline value. If an assessment occurs on the date of dosing, the time must occur prior to the time of dosing.

Variable	Baseline definition
Hematology, serum, chemistry, urinalysis	The baseline value is defined as the value on Day -1. If the baseline value is missing, the value obtained at Screening will be used.
Vital signs	The baseline value is defined as the last value prior to dosing.
ECG	12-lead ECG will be measured in triplicate. Baseline is the mean of the last three available measurements prior to dosing. If less than three replicates are available, the mean of the available replicates at the same visit (prior to dosing) will be considered as baseline.
C-SSRS	The baseline value is defined as the value from Day -1. If the baseline value is missing, the value obtained at Screening will be used.

The change from Baseline to any subsequent post-Baseline visit will be calculated as the simple difference between that post-Baseline visit’s value and the Baseline visit value, as below:

---

*Change from Baseline = Post Baseline Visit Value – Baseline Visit Value*

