1.3.1.2 Part 1 Sequence B

Table 1-5: Schedule of activities- Part 1 Treatment Sequence B

Day	Screening	Baseline	OC			Washout (14 Days)	PSL+OC						EOS/ SFU EDV ^a						
			1	2	3		18	19 to 20	21 to 22	23 to 29	30	31		32 to 33	34 to 35	36			
Written informed consent	X	-1																	
Demographics and baseline characteristics	X																		
Inclusion /Exclusion criteria verification	X	X	X				X												
General medical /medications/ procedures history	X	X					X (D17)												
Suicidality Risk Assessment (C-SSRS) ^b	X	X					X (D17)												X
Psychiatric and mental status evaluation	X	X						X	X	X	X	X	X	X	X	X	X	X	X
Physical examination ^c	X	X						X	X	X	X	X	X	X	X	X	X	X	X
Vital signs ^d	X	X						X	X	X	X	X	X	X	X	X	X	X	X
Pregnancy test	X	X						X (D17)											
Hematology, clinical chemistry, urinalysis	X	X					X (D17)												X
Serology (HIV, HbsAg, HEV, syphilis, and HCV-Ab)	X	X																	
12-lead ECG	X	X	X					X	X ^e	X ^e	X ^e	X ^e	X ^e	X ^e	X ^e	X ^e	X ^e	X ^e	X

Table 1-5: Schedule of activities- Part 1 Treatment Sequence B

	Screening	Baseline	OC			Washout (14 Days)	PSL+OC						EOS/ SFU EDV ^a		
			1	2	3		18	19 to 20	21 to 22	23 to 29	30 31	32 to 33		34 to 35	36
Day	-29 to -2	-1	1	2	3	4 to 17	18	19 to 20	21 to 22	23 to 29	30 31	32 to 33	34 to 35	36	43 to 46
Urine and cotinine drug screen, and alcohol breath test	X	X				X (D17)									
Recording of adverse events/medical procedures	X	X	X	X	X	X(D17)	X	X	X	X	X	X	X	X	X
Blood sampling for genotyping of drug metabolizing enzymes and/or transporters															
Admit to clinic		X				X(D17)									
Administer PSL							X	X	X	X	X	X	X	X	
Administer OC			X							X					
Blood sampling for PSL PK levels								X ^f	X ^f	X ^f	X ^f	X ^f			
Blood sampling for OC PK levels			X ^g	X ^g	X ^g					X ^g	X ^g	X ^g			
Blood sampling for cross-validation ^h										X					
Discharge					X										X (D37 or D38) ^j

C-SSRS=Columbia Suicide Severity Rating Scale; ECG=electrocardiogram; EDV= Early Discontinuation Visit; EOS=End of Study; h=hour(s); HbsAg-Ab=HepB surface antigen antibodies; HCV-Ab=HepC virus antibodies; HEV=hepatitis E virus; HIV=human immunodeficiency virus; OC=oral contraceptive; PK=pharmacokinetic; PSL=padsevonil; SFU=Safety Follow-Up

^a If a study participant discontinues early, SFU procedures should be completed as the EDV. Upon early termination/withdrawal, the study participant will be encouraged to complete SFU assessments following the last dose of study medication.

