9.2 General statistical considerations

Statistical evaluation will be performed by the Sponsor or designee and supervised by the Early Development Statistics Department of UCB. All statistical analyses will be performed using SAS[®] Version 9.4 or later (SAS Institute, Cary, NC, USA).

For continuous variables, summary statistics will include number of study participants, mean, median, standard deviation, minimum, and maximum (geometric mean and geometric coefficient of variation [CV] for plasma concentrations and PK parameters). Categorical endpoints will be summarized using number of study participants, frequency, and percentages. Missing data will not be imputed. Individual plasma concentration and PK parameters will be presented using three significant digits.

If not otherwise stated, Baseline will be the last assessment prior to dosing. Measurement of specific Baseline values will be described in the SAP.

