### 4.3 Handling of repeated and unscheduled measurements

All repeated and unscheduled measurements will be presented in the data listings, where applicable. The following general rules will apply to all repeated and unscheduled measurements:

- For repeated measurements obtained prior to the first dose of study medication the latest value (which may be scheduled or unscheduled) will be used in the calculation of the descriptive statistics
- For repeated measurements obtained at the designated Baseline visit, the latest value (which may be scheduled or unscheduled) will be defined as the Baseline provided that this occurred prior to the first dose of study medication
- Unscheduled and repeated measurements will not be used in the descriptive statistics at time points after first dose of study medication
- Unscheduled measurements performed for the End of Study/Safety-Follow-Up/Early Discontinuation Visit (EOS/SFU/EDV) visit will be assigned to the EOS/SFU/EDV Visit (Section 4.4) and analyzed accordingly as an EOS/SFU/EDV Visit.

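### The SAP's single pre-Day 1 safety baseline means that Sequence B changes on padsevonil are measured from before the OC dose and the 14-day washout, although Day 17 laboratory values are scheduled

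*SAP*

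**What the plan says.** The protocol sets a default in section 9.2, "If not otherwise stated, Baseline will be the last assessment prior to dosing", and leaves the details to the SAP.

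SAP 3.3 supplies them. The general rule is "Baseline will be the last non-missing value prior to first dosing on Day 1", and the SAP names the dose: "PSL dosing in Treatment Sequence A or OC dosing in Treatment Sequence B". The rows for individual variables then read:

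- Laboratory tests: "The baseline value is defined as the value on Day -1", with Screening as the fallback.
- Vital signs: "The baseline value is defined as the last value prior to dosing".
- ECG: "Baseline is the mean of the last three available measurements prior to dosing".

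The last two rows do not say which dose is meant. The general rule does, and so does SAP 4.3, where the latest repeat at the baseline visit "will be defined as the Baseline provided that this occurred prior to the first dose of study medication". Neither document resets the baseline by treatment period.

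In Part 1 Sequence B, OC is given on Day 1, washout runs from Day 4 to Day 17, and PSL is given from Day 18 to Day 36. In Protocol Table 1-5 (repeated as SAP Table 2-5), the row "Hematology, clinical chemistry, urinalysis" is marked at Day 17, and ECG and vital signs are scheduled on Day 18.

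Change from baseline feeds the laboratory change summaries and shift tables (SAP 10.3), the vital-sign TEMA/PCS flags (SAP 10.4.1 and Table 10-2) and the QTcF change categories (SAP 10.4.2).

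**The concern.** A change from baseline on PSL is meant to show what happened after PSL started. In Sequence A it does, because the reference sits immediately before the first PSL dose. In Sequence B the same quantity also carries the single OC dose, two weeks away from the clinic and ordinary drift over that time. A shift or flag on PSL therefore does not have the same meaning in the two sequences.

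Elsewhere the SAP is anchored to treatment. SAP 3.2.1 counts relative days for PSL from Day 18 in Sequence B, and SAP 10.2 attributes adverse events to the treatment after which they start. The baseline is the exception. A better laboratory reference has already been scheduled, one day before PSL, and is not used as one.

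**Working it through.** **Inputs.** There is no Day 0: Protocol 1.1.5 makes Day -1 the day before Day 1, and SAP 3.2.1 excludes a relative Day 0. The days below come from SAP 3.2.1, 3.2.2 and 3.3, and from Protocol Tables 1-4 and 1-5.

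| Item | Sequence A | Sequence B |
|---|---|---|
| First PSL dose | Day 1 | Day 18 |
| Laboratory baseline | Day -1 | Day -1 |
| Earliest and latest usual vital-sign or ECG baseline | Day -1 or Day 1 predose | Day -1 or Day 1 predose |
| Laboratory draw on last PSL day, Part 1 | Day 19 | Day 36 |
| Scheduled laboratory draw just before PSL | Day -1 | Day 17 |

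**Formula.** Elapsed days between two positive days are end minus start. When the start is Day -1, subtract one more because Day 0 does not exist.

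**The plan's own figure.** Washout in Sequence B, Days 4 to 17 inclusive: 17 - 4 + 1 = 14 days. This agrees with the stated 14 days.

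**Baseline to first PSL dose.**

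- Sequence A, from Day -1: 1 - (-1) - 1 = 1 day. From a Day 1 predose value: 0 days.
- Sequence B, from Day -1: 18 - (-1) - 1 = 18 days. From a Day 1 predose value: 18 - 1 = 17 days.
- Sequence B laboratory tests when Day -1 is missing and Screening (Day -29 to Day -2) is used: 18 - (-2) - 1 = 19 days up to 18 - (-29) - 1 = 46 days.

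**Span of the end-of-PSL laboratory change, Part 1.**

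- Sequence A, Day -1 to Day 19: 19 - (-1) - 1 = 19 days.
- Sequence B as planned, Day -1 to Day 36: 36 - (-1) - 1 = 36 days.
- Sequence B from Day 17: 36 - 17 = 19 days.

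The excess in Sequence B is 36 - 19 = 17 days. This is the OC-alone days (Days 1 to 3, 3 days) plus the washout (14 days). A Day 17 baseline removes exactly that excess.

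**What is firm for each variable.** The Day 17 laboratory draw precedes PSL by a day, so it qualifies without further conditions. Vital signs and ECG are less certain. They are scheduled on Day 18, but neither document says that they are taken before the morning PSL dose. They qualify only where the recorded time is predose, a condition that SAP 3.3 already applies to assessments on a dosing day.

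**The case against.** The strongest defence is that one study baseline is a legitimate choice. The protocol labels Day -1 as Baseline and leaves the specifics to the SAP, so the documents do not contradict each other. A value taken before any study drug is the only fully unexposed reference. The tables are also largely self-correcting. Laboratory, vital-sign and ECG changes are shown by sequence and time point, and Day 17 is itself a post-baseline laboratory time point in Sequence B, so any drift before PSL will be visible. All of this stands. It is why the existing baseline should be kept and why the point is minor. It does not supply the change from just before PSL to the end of PSL within a participant, which a reader would have to reconstruct.

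Four stronger readings are tempting, and the documents do not support them:

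- **The two sequences cannot be pooled.** SAP 10.3, 10.4.1 and 10.4.2 plan these summaries by sequence, and the table in SAP 13 marks them under Sequence only. SAP 3.6 mentions an overall presentation in general terms. On a given study day, however, the sequences are mostly on different treatments, so an overall column by day would mix treatments whatever the baseline.
- **A large gain in precision.** For equal variances, the SD of change with the near baseline relative to the distant one is the square root of (1 - r_near)/(1 - r_far), where r is the correlation with the on-PSL value. Neither document gives a correlation. If the two are equal, the ratio is 1 and there is no gain, so no percentage can be claimed.
- **The same remedy for Sequence A, with a Day 33 baseline for OC alone.** That value follows 19 days of PSL and could hide a persisting PSL effect.
- **The same remedy for C-SSRS.** SAP 10.4.3.2 only lists the scale, so a new baseline would change no summary.

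**Conclusion.** The point holds as a minor weakness in an analysis definition. In Sequence B, changes on PSL are referred to a value 18 days before first PSL for laboratory tests and 17 to 18 days before for vital signs and ECG. In Sequence A the gap is at most 1 day. The Part 1 end-of-PSL laboratory change covers 36 days in one sequence and 19 in the other. These counts assume attendance on the scheduled days and a non-missing Day -1 laboratory value.

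The reach is small. Laboratory, vital-sign and ECG changes are descriptive endpoints in the Other category, and the TEMA/PCS criteria only flag results. SAP 1 restricts reporting to Part 1 and to a subset of outputs. The primary PK comparison and the treatment-emergent adverse event summaries do not use this baseline. A reader might infer that the safety conclusions are biased; the documents show unequal reference points, not a bias of known size or direction.

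**What to change.** In SAP 3.3, add a pre-PSL baseline for Sequence B:

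- Laboratory tests: the Day 17 value.
- Vital signs: the last value with a recorded time before the first PSL dose on Day 18.
- ECG: the mean of the last triplicate with a recorded time before that dose.
- Where no such predose vital sign or ECG exists, keep the study baseline and footnote it.

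Use this baseline for the Sequence B on-PSL laboratory change and shift tables, the vital-sign TEMA/PCS flags and the QTcF change categories. Keep the Day -1 or Day 1 predose baseline beside it as the unexposed reference. State in the vital-sign and ECG rows which dose is meant, so that the wording cannot be read as a reset in each period. Leave Sequence A and C-SSRS as they are.

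The cost is a paragraph of SAP text, a second baseline flag and some extra table columns. No new data are needed for laboratory tests. For vital signs and ECG, the benefit depends on how many Day 18 records carry a predose time.

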### **3.4 Protocol deviations**

Important protocol deviations (IPD) are deviations from the protocol which potentially could have a meaningful impact on study conduct or on the primary PK outcome for an individual study participant. Study participants will be excluded from SS only when there is documented evidence that they received no treatment. Study participants may be excluded from the Pharmacokinetic Set (PKS) if they had an important protocol deviation affecting the PK parameters.

The criteria for identifying protocol deviations and the classification of protocol deviations will be captured in the Important Protocol Deviations document. To the extent feasible, rules for identifying protocol deviations will be defined without review of the data and without consideration of the frequency of occurrence of such deviations. Whenever possible, criteria for identifying important protocol deviations will be implemented algorithmically to ensure consistency in the classification of important protocol deviations across all study participants.

Important protocol deviations will be reviewed as part of an ongoing data cleaning process prior to database lock to confirm exclusion from analysis sets. After all data have been verified/coded/entered into a database, a data evaluation meeting (DEM) will be held.

At least one DEM will be performed at the following time:

- Prior to the final analysis after all data have been verified/coded/entered into the database

Additional DEMs may be conducted as deemed necessary.

The purpose of these DEM reviews will be to review all protocol deviations, determine whether the deviations are considered important or not important, define the analysis sets, and check the quality of the data. The reviews will also help decide how to manage problems in the study participants' data (e.g., missing values, withdrawals and protocol deviations).

Accepted deviations from scheduled time points will be described in the appropriate documents and included in the Study Master File. After the pre-analysis review, resolution of all issues, and documentation of all decisions (including inclusion into each of the analysis sets) at the final DEM, the database will be locked.

### **3.5 Analysis sets**

#### **3.5.1 All Study Participants**

All Study Participants consists of all study participants who have signed the Informed Consent Form (ICF).

#### **3.5.2 Safety Set (SS)**

The Safety Set (SS) consists of all study participants who received at least one dose of study medication (PSL or OC).

---

### 3.5.3 Pharmacokinetic Set (PKS)

The Pharmacokinetic Set (PKS) is a subset of the SS, consisting of those study participants who had no important protocol deviations affecting the PK parameters of EE, LN, or PSL and its metabolites and for whom at least one measurable concentration exists.

### 3.6 Treatment assignment

It is expected that study participants will receive treatments as per the randomized treatment sequence and hence the analyses will be based on the randomized treatment. If a study participant was randomized but not dosed in any treatment period, the study participant results will be reported under the randomized treatment group. For safety analyses based on the SS, study participants will be classified according to the medication that was actually received.

Except for PK, concomitant medications, and adverse events, tables will be presented separately for each study part by randomized Treatment Sequence (Sequence A: PSL+ OC followed by OC alone and Sequence B: OC alone followed by PSL+OC) and overall. Listings will be presented by study part, randomized treatment sequence, and study participant number. PK summaries will be presented by study part, treatment period (OC alone and OC+PSL), and analyte (EE, LN; PSL and its metabolites). Concomitant medication and adverse event tables will be presented separately for each study part by treatment (OC alone, PSL alone, and OC+PSL).

A detailed schematic diagram of the study is provided in [Table 2-2](#) and [Table 2-3](#).

